### **3) Contraceptive Requirements for Male Subjects**

It is theoretically possible that a relevant systemic concentration may be achieved in a female partner from exposure of the male subject's seminal fluid. Therefore, male subjects with female partners of childbearing potential must use condoms during treatment until 90 days after the last dose of the study drugs.

Male subjects must refrain from sperm donation from clinic admission, throughout the study period, and continuing for at least 90 days following the last dose of study drugs.

### **4) Unacceptable Birth Control Methods**

Birth control methods that are unacceptable include periodic abstinence (eg, calendar, ovulation, symptothermal, post-ovulation methods), withdrawal (coitus interruptus), spermicide only, and lactational amenorrhea method (LAM). Female condom and male condom should not be used together.

### **5) Procedures to be Followed in the Event of Pregnancy**

Subjects will be instructed to notify the investigator if they become pregnant at any time during the study, or if they become pregnant within 30 days (90 days of partner of male subject) of last study drug dose. Subjects who become pregnant or who suspect that they are pregnant during the study must report the information to the investigator and discontinue study drugs immediately. Subjects whose partner has become pregnant or suspects she is pregnant during the study must report the information to the investigator. Instructions for reporting pregnancy, partner pregnancy, and pregnancy outcome are outlined in Section 7.6.2.

**Appendix 4. Common Terminology Criteria for Adverse Events (CTCAE) Version 4.0**

[http://evs.nci.nih.gov/ftp1/CTCAE/CTCAE\\_4.03\\_2010-06-14\\_QuickReference\\_8.5x11.pdf](http://evs.nci.nih.gov/ftp1/CTCAE/CTCAE_4.03_2010-06-14_QuickReference_8.5x11.pdf)

DMC	data monitoring committee
ECG	electrocardiogram
eCRF	electronic case report form
eGFR	estimated glomerular filtration rate
ELF	enhanced liver fibrosis
ET	early termination
EOT	end of treatment
FAS	Full Analysis Set
FU	follow-up
GGT	uric acid Gamma-glutamyl transferase
GSI	Gilead Sciences, Inc.
HbA1c	hemoglobin A1c
HCV	hepatitis C virus
HDL	high-density lipoprotein
HDL-C	HDL-cholesterol
HLT	high level term
HLGT	high level group term
HOMA-IR	homeostasis model assessment of insulin resistance
ID	identification
IND	Investigational New Drug (Application)

INR	international normalized ratio
IXRS	interactive voice/web response system
LDH	lactate dehydrogenase
LDL-C	low-density lipoprotein cholesterol
LLT	lower level term
LLOQ	lower limit of quantitation
MedDRA	medical dictionary for regulatory activities
MRE	magnetic resonance elastography
MRI-PDFF	magnetic resonance imaging – proton density fat fraction
NASH	nonalcoholic steatohepatitis
PE	physical examination
PK	pharmacokinetic
PT	preferred term
Q1	first quartile
Q3	third quartile
QoL	quality of life
RBC	red blood cell
RNA	Ribonucleic acid
SAE	serious adverse event
SAP	statistical analysis plan
SBP	systolic blood pressure
SD	standard deviation
SOC	system organ class
TE	treatment-emergent
TFLs	tables, figures, and listings
ULN	upper limit of normal
ULOQ	upper limit of quantitation
VLDL-C	very low density lipoprotein-cholesterol
WBC	white blood cell
WHO	World Health Organization
WPAI	work productivity and activity impairment questionnaire

PHARMACOKINETIC ABBREVIATIONS

AUC _{last}	area under the concentration versus time curve from time zero to the last quantifiable concentration
AUC _{tau}	area under the concentration versus time curve over the dosing interval
C _{last}	last observed quantifiable concentration of the drug
C _{max}	maximum observed concentration of drug
C _{tau}	observed drug concentration at the end of the dosing interval
CLss/F	apparent oral clearance after administration of the drug: at steady state: $CLss/F = Dose/AUC_{tau}$, where “Dose” is the dose of the drug
t _{1/2}	estimate of the terminal elimination half-life of the drug, calculated by dividing the natural log of 2 by the terminal elimination rate constant (λ_z)
T _{last}	time (observed time point) of C _{last}
T _{max}	time (observed time point) of C _{max}
λ_z	terminal elimination rate constant, estimated by linear regression of the terminal elimination phase of the concentration of drug versus time curve

1. INTRODUCTION

This statistical analysis plan (SAP) describes the statistical analysis methods and data presentations to be used in tables, figures, and listings (TFLs) in the clinical study report (CSR) for Study GS-US-426-3989. This SAP is based on the study protocol Amendment 1.1 dated 19 December 2016 and the electronic case report form (eCRF). The SAP will be finalized before database finalization. Any changes made after the finalization of the SAP will be documented in the CSR.

1.1. Study Objectives

The primary objective of this study is as follows:

- To evaluate the safety and tolerability of GS-0976 in subjects with nonalcoholic steatohepatitis (NASH).

The exploratory objectives of this study are as follows:

1.2. Study Design

1.2.1. Design Configuration, Subject Population and Treatment Groups

This is a Phase 2, randomized, double-blind, placebo-controlled study designed to evaluate the safety, tolerability, and efficacy of GS-0976 in subjects with NASH. To be eligible to participate, subjects must have evidence of hepatic steatosis and increased liver stiffness as assessed by MRI-PDFF and MRE, respectively, or a historical liver biopsy consistent with NASH and noncirrhotic fibrosis. Any subject with history of decompensated liver disease, including ascites, hepatic encephalopathy, or variceal bleeding, will be ineligible.

Subjects meeting the study's entry criteria will be randomly assigned in a 2:2:1 ratio to 1 of 3 different treatment groups, A, B, and C, respectively:

- Group A (n = 50): GS-0976 5 mg (1 × 5 mg + PTM 5 mg + 2 × PTM 10 mg), orally once daily;
- Group B (n = 50): GS-0976 20 mg (2 × 10 mg + 2 × PTM 5 mg), orally once daily;
- Group C (n = 25): GS-0976 Placebo (2 × PTM 5 mg + 2 × PTM 10 mg), orally once daily.

Randomization will be stratified by the presence or absence of diabetes mellitus as determined by medical history, or based on Screening or Baseline/Day 1 lab values prior to first dosing if previously undiagnosed (ie, hemoglobin A1c \geq 6.5% or fasting glucose \geq 126 mg/dL).

1.2.2. Study Duration

The total time to complete all study visits is up to approximately 22 weeks including the following periods:

- 6-week screening period
- 12-week treatment period
- 4-week follow-up period

1.2.3. Schedule of Assessments

The schedule of assessments is provided as an appendix to the SAP ([Appendix 1](#)). After the Screening period and a randomization visit at Baseline/Day 1, study visits will occur at Weeks 1, 4, 8, 12, and a Follow-Up visit 4 weeks after the last dose of study drug. At minimum, vital sign measurements, symptom-driven physical examinations (PEs), safety laboratory tests (blood chemistry, hematology, coagulation panel, and lipid profile), and review of adverse events (AEs) and concomitant medications (CMs) will be done at every visit. Refer to [Appendix 1](#) for details.

1.3. Sample Size and Power

Due to the exploratory nature of this study, no formal power calculations were used to determine sample size. The number of subjects was chosen based on clinical experience with other similar proof-of-concept studies. However, assuming that 4% of subjects in the Placebo arm (N = 25) and 32% in the GS-0976 20 mg arm (N = 50) have a \geq 30% reduction in MRI-PDFF at Week 12, this sample size will provide 80% power to detect the difference between GS-0976 and Placebo based on a 2-sided Fisher's exact test at a significance level of 0.05.

2. TYPE OF PLANNED ANALYSIS

2.1. Interim Analyses

2.1.1. Data Monitoring Committee Analyses

An external multidisciplinary Data Monitoring Committee (DMC) will review the progress of the study and perform interim reviews of safety data in order to protect subject welfare and preserve study integrity. The DMC is to recommend whether the nature, frequency, and severity of adverse effects associated with study treatment warrant the early termination of the study in the best interests of the participants, whether the study should continue as planned, or whether the study should continue with modifications.

The first DMC review will be conducted after approximately 20 subjects have been enrolled and every 3 to 4 months thereafter to monitor the study for safety events until all randomized subjects complete or discontinue the study. The DMC will meet on an ad hoc basis if there are at least 3 Grade 3 or higher serious, treatment-related adverse events (AEs) observed in the study, based on the Common Terminology Criteria for Adverse Events (CTCAE). In the event of two similar Grade 4-CTCAE treatment-related adverse events or one Grade 5-CTCAE treatment-related adverse event, the DMC will review the data and advise regarding stopping or continuing the study.

The DMC's role and responsibilities and the scope of analysis to be provided to the DMC are provided in a mutually agreed upon charter, which defines the DMC membership, meeting logistics, and meeting frequency.

2.1.2. Interim Analysis

There is no interim analysis planned for this study.

2.2. Final Analysis

After all subjects have completed the study, outstanding data queries have been resolved or adjudicated as unresolvable, and the data have been cleaned and finalized, the study blind will be broken and the final analysis of the data will be performed.

3. GENERAL CONSIDERATIONS FOR DATA ANALYSES

Analysis results will be presented using descriptive statistics. For categorical variables, the number and percentage of subjects in each category will be presented; for continuous variables, the number of subjects (n), mean, standard deviation (SD), median, first quartile (Q1), third quartile (Q3), minimum, and maximum will be presented.

Data collected in the study will be presented in by subject listings for all subjects in the specified analysis set and will be sorted by subject ID number, visit date, and time (if applicable), unless otherwise specified. Data collected on log forms, such as AEs, will be presented in chronological order for each subject.

3.1. Analysis Sets

Analysis sets define the subjects to be included in an analysis. Analysis sets and their definitions are provided in this section. The analysis set will be identified and included as a subtitle of each table, figure, and listing.

For each analysis set, the number and percentage of subjects eligible for inclusion, as well as the number and percentage of subjects who were excluded and the reasons for their exclusion, will be summarized. Percentage will be calculated in proportion to the number of subjects in the all randomized analysis set by treatment group.

A listing of reasons for exclusion from analysis sets will be provided by subject.

3.1.1. All Randomized Analysis Set

The All Randomized Analysis Set includes all subjects who were randomized into the study.

3.1.2. Full Analysis Set

The Full Analysis Set (FAS) includes all subjects who were randomized into the study and took at least 1 dose of study drug. This is the primary analysis set for efficacy analyses.

3.1.3. Safety Analysis Set

The Safety Analysis Set includes all subjects who took at least 1 dose of study drug. This is the primary analysis set for safety analyses.

3.1.4. Pharmacokinetic Analysis Set

The Pharmacokinetic (PK) Analysis Set will include all randomized subjects who took at least 1 dose of study drug and have at least 1 nonmissing postdose concentration value reported by the PK laboratory.

This is the primary analysis set for all PK analyses.

3.1.5.

CCI

3.2.

Subject Grouping

For analyses based on the All Randomized Analysis Set or FAS, subjects will be grouped according to the treatment to which they were randomized. For analyses based on the Safety Analysis Set, subjects will be grouped according to actual treatment received. The actual treatment received will differ from the randomized treatment only when their actual treatment differs from randomized treatment for the entire treatment duration.

Treatment groups GS-0976 20 mg and GS-0976 5 mg will be combined together as group GS-0976 pooled for analysis based on Safety Analysis Set. The summary will be prepared by treatment groups in the order of GS-0976 20 mg, GS-0976 5 mg, GS-0976 pooled, and Placebo.

3.3.

Strata and Covariates

Subjects will be randomly assigned to treatment groups via the interactive web response system (IXRS) in a 2:2:1 ratio using a stratified randomization schedule. Stratification will be based on the presence or absence of diabetes mellitus.

If there are discrepancies in stratification factor values between the IWRS and the clinical database, the baseline values recorded in the clinical database will be used for analyses, which is determined by medical history, or based on lab values (either Screening or Baseline/Day 1 value prior to first dosing) if previously undiagnosed (ie, hemoglobin A1c $\geq 6.5\%$ or fasting glucose ≥ 126 mg/dL).

3.4.

Examination of Subject Subgroups

Subgrouping of subjects based on randomization stratification factor will be explored for subgroup analyses. The subgroups are as follows:

- presence of diabetes mellitus
- absence of diabetes mellitus

3.5.

Multiple Comparisons

Adjustments for multiplicity will not be made because no formal statistical testing will be performed in this study. Any p-values displayed are for exploratory purposes only.

3.6. Missing Data and Outliers

3.6.1. Missing Data

In general, missing data will not be imputed unless methods for handling missing data are specified. Exceptions are presented in this document.

For missing MRI-PDFF, imputation rules are specified in Section 6.2.3. For missing last dosing date of study drug, imputation rules are described in Section 4.2.1. The handling of missing or incomplete dates for AE onset is described in Section 7.1.5.2, and for prior and concomitant medications in Section 7.4.

3.6.2. Outliers

Outliers will be identified during the data management and data analysis process, but no sensitivity analyses will be conducted. All data will be included in the data analysis.

3.7. Data Handling Conventions and Transformations

In general, age (in years) on the date of the first dose of study drug will be used for analyses and presentation in listings. If an enrolled subject was not dosed with any study drug, the randomization date will be used instead of the first dosing date of study drug. For screen failures, the date the informed consent was signed will be used for age calculation. If only birth year is collected on the case report form (CRF), “01 July” will be used for the unknown birth day and month for the purpose of age calculation. If only birth year and month are collected, “01” will be used for the unknown birth day.

Non-PK data that are continuous in nature but are less than the lower limit of quantitation (LOQ) or above the upper LOQ will be imputed as follows:

- A value that is 1 unit less than the LOQ will be used for calculation of descriptive statistics if the datum is reported in the form of “ $< x$ ” (where x is considered the LOQ). For example, if the values are reported as < 50 and < 5.0 , values of 49 and 4.9, respectively, will be used for calculation of summary statistics. An exception to this rule is any value reported as < 1 or < 0.1 , etc. For values reported as < 1 or < 0.1 , a value of 0.9 or 0.09, respectively, will be used for calculation of summary statistics.
- A value that is 1 unit above the LOQ will be used for calculation of descriptive statistics if the datum is reported in the form of “ $> x$ ” (where x is considered the LOQ). Values with decimal points will follow the same logic as above.
- The LOQ will be used for calculation of descriptive statistics if the datum is reported in the form of “ $\leq x$ ” or “ $\geq x$ ” (where x is considered the LOQ).

If methods based on the assumption that the data are normally distributed are not adequate, analyses may be performed on transformed data or nonparametric analysis methods may be used, as appropriate.

Natural logarithm-transformation will be used for blood concentrations and analysis of PK parameters. Plasma concentration values that are below the limit of quantitation (BLQ) will be presented as “BLQ” in the concentration data listing. Values that are BLQ will be treated as 0 at predose time points, and one-half the value of the LLOQ at postbaseline time points.

The following conventions will be used for the presentation of summary and order statistics:

- If at least 1 subject has a concentration value of BLQ for the time point, the minimum value will be displayed as “BLQ.”
- If more than 25% of the subjects have a concentration data value of BLQ for a given time point, the minimum and Q1 values will be displayed as “BLQ.”
- If more than 50% of the subjects have a concentration data value of BLQ for a given time point, the minimum, Q1, and median values will be displayed as “BLQ.”
- If more than 75% of the subjects have a concentration data value of BLQ for a given time point, the minimum, Q1, median, and Q3 values will be displayed as “BLQ.”
- If all subjects have concentration data values of BLQ for a given time point, all order statistics (minimum, Q1, median, Q3, and maximum) will be displayed as “BLQ.”

3.8. Analysis Visit Windows

3.8.1. Definition of Study Day

Study day is the day relative to the date of the first dose of study drug. Study Day 1 will be defined as the day of first dose of study drug administration.

Study day will be calculated from the date of first dose of study drug administration and derived as follows:

- For postdose study days: Assessment Date – First Dosing Date + 1
- For days prior to the first dose: Assessment Date – First Dosing Date

If the last dosing date of study drug is missing or incomplete, the date of last dose will be estimated using the maximum of nonmissing study drug start or stop dates, visit dates, and laboratory collection dates (posttreatment visits and unscheduled visits are not included).

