4.2.1. Duration of Exposure to Study Drug

Total duration of exposure to study drug will be defined as last dosing date minus first dosing date plus 1, regardless of any temporary interruptions in study drug administration, and will be expressed in weeks using up to 1 decimal place (e.g., 4.5 weeks). If the last study drug dosing date is missing, the latest date among the study drug end date, clinical visit date, laboratory sample collection date, and vital signs assessment date that occurred during the on-treatment period will be used.

Total duration of exposure to study drug (weeks) = (last dose date - first dose date + 1)/7

The total duration of exposure to study drug will be summarized using descriptive statistics (sample size, mean, SD, median, Q1, Q3, minimum, and maximum) and using the number (ie, cumulative counts) and percentage of subjects exposed through the following time points: 1 day, 1 week, 4 weeks, 8 weeks, and 12 weeks.

Summaries will be provided by treatment group for the Safety Analysis Set.

No formal statistical testing is planned.

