7.1.5. Treatment-Emergent Adverse Events

7.1.5.1. Definition of Treatment-Emergent Adverse Events

Treatment-emergent adverse events (TEAEs) are defined as 1 or both of the following:

- Any AEs with an onset date on or after the study drug start date and no later than 30 days after permanent discontinuation of study drug
- Any AEs leading to premature discontinuation of study drug.

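### The SAP gives two different imputation rules for the last-dose date, and the only one that covers an incomplete date ignores the recorded month and year, so the +30-day safety windows can close weeks early

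*SAP*

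**What the plan says.** Two SAP sections impute the same variable.

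- **SAP 3.8.1** is triggered as follows: "If the last dosing date of study drug is missing or incomplete". In that case "the date of last dose will be estimated using the maximum of nonmissing study drug start or stop dates, visit dates, and laboratory collection dates", and it adds that "posttreatment visits and unscheduled visits are not included".
- **SAP 4.2.1** is triggered by a missing date only. It takes "the latest date among the study drug end date, clinical visit date, laboratory sample collection date, and vital signs assessment date", limited to records in the on-treatment period. It does not exclude unscheduled visits and does not mention incomplete dates.
- **SAP 3.6.1** sends the reader to one of the two: "For missing last dosing date of study drug, imputation rules are described in Section 4.2.1".

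The date feeds the primary safety outputs. A treatment-emergent adverse event has its onset "no later than 30 days after permanent discontinuation of study drug" (SAP 7.1.5.1), and 7.1.5.2 counts those 30 days from the last dose. Laboratory abnormalities (7.2.2), liver-related summaries (7.2.3) and general visit mapping (3.8.2) also run to last dose plus 30 days.

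**The concern.** Safety is the primary endpoint, and the last-dose date decides which events and laboratory values enter the summary tables. Two programmers working from different sections could derive different window ends for one subject, and the text does not say which is right outside the exposure calculation.

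The incomplete-date case is the more serious one. A site may know that dosing ended in a given month but not on which day. SAP 3.8.1 replaces that information with the last scheduled contact, even when this falls in an earlier month. Elsewhere the SAP does use recorded month and year: for adverse event onset in 7.1.5.2 and for medication dates in 7.4. Subjects with an uncertain stop date are likely to be those who stopped irregularly, for whom late events are of interest. Choosing a rule after unblinding would be a post hoc decision.

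**Working it through.** **1. The rules side by side**

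| | SAP 3.8.1 | SAP 4.2.1 |
|---|---|---|
| Trigger | missing or incomplete | missing only |
| Drug record dates | start or stop | end only |
| Visit and laboratory dates | yes | yes |
| Vital-signs dates | not listed | yes |
| Unscheduled visits | excluded | not excluded |
| Posttreatment records | excluded by name | excluded only through the on-treatment period |
| Recorded month and year | not used | not addressed |

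The on-treatment period is not defined in the available SAP text. Its natural definition ends at the last dose, which is the date being imputed, so the 4.2.1 rule is circular.

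**2. Inputs for the arithmetic**

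The nominal day for Week x is 7x + 1 (SAP 3.8.3), which gives Days 8, 29, 57 and 85. Window end = imputed last dose + 30 days. Protocol 6.4.5 allows unscheduled visits during treatment, including visits only to supply drug. The unscheduled days and calendar dates below are illustrations.

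**3. Fully missing date**

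- Latest record is the Week 4 visit, Day 29. Both rules give Day 29, so the difference is 0.
- Week 4 visit on Day 29, then an unscheduled on-drug visit on Day 36. SAP 3.8.1: 29 + 30 = Day 59. SAP 4.2.1: 36 + 30 = Day 66. The difference is 7 days. An event with onset on Day 62, reported at a later contact, is treatment-emergent under one rule only.
- Week 8 visit on Day 57, then an unscheduled visit on Day 78. Window ends are 57 + 30 = Day 87 and 78 + 30 = Day 108. The difference is 21 days.

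**4. Incomplete date**

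First dose on 10 January 2017 (Day 1), Week 4 visit on 7 February (Day 29), last dose recorded only as March 2017, and no later scheduled or complete drug record.

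- SAP 3.8.1 imputes 7 February, before the recorded month. The window closes on 9 March.
- The earliest date consistent with the record is 1 March (Day 51). The window would close on 31 March or later.
- The shortfall is at least 51 − 29 = 22 days.
- If the last dose was on 6 March (Day 56, the day before the nominal Week 8 visit), the shortfall is 56 − 29 = 27 days.

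**5. Bound**

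If dosing stopped before the next scheduled visit, the shortfall is limited by the visit gap: 57 − 29 = 28 days and 85 − 57 = 28 days, or about 4 weeks. At the extremes of the visit tolerances the gaps are (57 + 3) − (29 − 3) = 34 days and (85 + 7) − (57 − 3) = 38 days.

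**6. The opposite direction**

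The schedule lists early termination with Week 12 under on-treatment visits. If dosing stopped on Day 31 and an early termination visit on Day 55 were accepted as on-treatment under 4.2.1, the imputed date would be 55 − 31 = 24 days late.

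**The case against.** The strongest reply is that 4.2.1 governs. SAP 3.6.1 names it for a missing date, exposure is defined only there, and 3.8.1 sits under visit windows. A reader might infer that the same subject gets two exposure durations, such as 29/7 = 4.1 and 36/7 = 5.1 weeks. The documents do not support that, because the shorter figure requires 3.8.1 to be applied to a table with its own rule. What remains is that 3.8.1 still states a different rule for a missing date, and that 4.2.1 offers none for an incomplete one. For incomplete dates the fault is therefore an override in one section and a gap in the other, not two competing numbers.

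Second, the on-treatment period in 4.2.1 could be read as the scheduled on-treatment visits, since the schedule has no column for unscheduled ones. That reading is possible and would remove the visit-based conflict, but the text does not state it.

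Third, an early termination visit after stopping is posttreatment in plain meaning, which 3.8.1 excludes. This is fair for 3.8.1; 4.2.1 has no such wording.

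Fourth, a reader might infer that late events vanish. They do not. All adverse events are listed with a treatment-emergent flag, all deaths enter the overall summary, events leading to discontinuation are treatment-emergent whatever the window (SAP 7.1.5.1 and 7.1.6), and laboratory results are listed by subject (7.2). The loss is from summary tables only.

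Finally, stop dates are required source data (protocol 9.1.5), pill counts are made at each on-treatment visit, and queries are settled before unblinding (SAP 2.2). Few dates should stay unresolved.

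**Conclusion.** The point holds as a conditional one. The two rules differ in trigger, sources and treatment of unscheduled visits, and they can give different dates when the latest on-drug record is unscheduled (or is a separate vital-signs record). They agree when a fully missing date follows a scheduled visit. For an incomplete date the only available rule can impute a date before the recorded month, which closes the safety windows early by up to about 4 weeks. That bound assumes nominal visit spacing and no dosing beyond the next scheduled visit.

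The number of subjects affected is unknown and probably small. The documents give no rate of missing or partial dates, so any count out of 125 would rest on an assumed rate. This is a minor correction, but it touches the primary safety tables and should be settled before unblinding.

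**What to change.** Keep one rule in SAP 4.2.1 for every use of the last-dose date, and replace the 3.8.1 text with a reference to it. The rule should:

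- keep a partial date within its recorded month and year: the latest on-treatment record in that month, otherwise the end of the month, capped at the early termination, Follow-Up or death date;
- for a fully missing date, include unscheduled visits that occur before known discontinuation;
- state that an early termination visit held after dosing stopped is not used as the last-dose date;
- define the on-treatment period without reference to the date being imputed.

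The cost is SAP wording and one derivation program. If the SAP is already final, its Section 1 requires the change to be documented in the study report. The downside is that month-end imputation may overstate exposure for a few subjects, and a Follow-Up visit 4 weeks after the last dose is a loose cap. For the safety window this errs in the conservative direction.
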